4.11.3.3. FCS Symptoms

The FCS Symptoms Questionnaire includes 4 items addressing the severity of abdominal pain, physical fatigue, difficulty thinking and diarrhea. These 4 items are administered on a daily basis and ask patients to rate the worst severity of each symptom in the past 24 hours using a 0–10 numeric rating scale. Higher scores denote more severe symptoms.

The daily symptom composite score will be calculated as the average of the non-missing scores across the 4 symptom items. If two or more questions are missing, the symptom composite score will be considered as missing for the day. If one item is missing, then the composite score will be calculated as the average of the 3 non-missing item scores

The data will be mapped to study week based on the visit window specified in Section 4.2.4. The data in the visit window will be averaged and used for summary and analysis. In addition to the weekly average, the highest (worst) response in each week will also be determined and used for summary and analysis. If patients complete less than 4 daily assessments in a week, then the weekly FCS symptom scores will be considered as missing for the week.

Item-level scores and the symptom composite scores, as well as their changes from baseline will be summarized by treatment group and by study week over time using descriptive statistics.

A summary of abdominal pain using the following categories will also be provided: no pain (pain score: 0), mild (pain score: > 0-3), moderate (pain score: > 3-6), or severe (pain score: > 6-10). The frequency and percentage in each category will be tabulated by treatment group and by study week over time.

The change from baseline in the weekly average item and composite scores at the primary analysis time point (average of Weeks 23 to 27) and at Month 12 (average of Weeks 49 to 53) as well as change from baseline in the highest (worst) item and composite scores at the primary analysis time point (worst of Weeks 23 to 27) and at Month 12 (worst of Weeks 49 to 53) will be analyzed using an ANCOVA model with the two stratification factors and treatment group as factors and the corresponding baseline score as a covariate, and will be conducted in the FAS.

The analyses described above will also be repeated using the corresponding FCS symptom collected at the two-week recall administered the first day of screening as the baseline.

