The item and composite scores will be imputed separately

• The Month 6 (primary analysis time point) score will be calculated from the non-missing weekly scores from Weeks 23 to 27 and the Month 12 score will be calculated from the non-missing weekly scores from Weeks 49 to 53. If all weekly scores during the period are missing, the missing score at the primary analysis time point will be imputed using the data from the week that is the closest to Day 169 and within a ± 30 days window, the missing Month 12 data will be imputed using the data from the week that is the closest to the Day 351 and within a ± 30 days window. If 2 or more visits with equal distance, then the average or worst will be used. The item and composite scores will be imputed separately.

ISIS 678354-CS3

Statistical Analysis Plan

The tables below list the summaries and analyses to be performed for the FCS symptom item and composite scores

Observed Data			
Endpoint	Baseline	Post-baseline	Analysis
Average FCS Symptom – item score and composite score	Baseline is defined as the average during the screening period and up to Day 1. If all assessments during the period are missing, the baseline will be considered as missing	Weekly average. If a patient has less than 4 assessments in a week, the weekly score will be considered as missing	 Descriptive statistics of score, change and percent change over time in the FAS Frequency of patients by abdominal pain category (no pain, mild, moderate and severe) over time in the FAS
		Month 6 (Primary analysis time point) - average of Weeks 23 to 27 Month 12 -average of Weeks 49 to 53	 Descriptive statistics of score, change and percent change at Month 6 and Month 12 in the FAS ANCOVA model of change from baseline with the two stratification factors and treatment group as factors, and the corresponding baseline score as a covariate in the FAS Descriptive statistics of abdominal pain score, change and percent change at Month 6 and Month 12 in the subset of FAS patients who reported any abdominal pain (pain score > 0) at Baseline ANCOVA model of change from baseline in abdominal pain score with the two stratification factors and treatment group as factors and the baseline score as a covariate in the subset of FAS patients who reported any abdominal pain (pain score > 0) at Baseline

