	Baseline is defined as the single observation collected at the first day of screening with a two-week recall	Weekly average. If a patient has less than 4 assessments within a week, the weekly score will be considered as missing	Descriptive statistics of score, change and percent change over time in the FAS

ISIS 678354-CS3

Observed Data			
Endpoint	Baseline	Post-baseline	Analysis
Average FCS Symptom – item score and composite score (Continued	Baseline is defined as the single observation collected at the first day of screening with a two-week recall (Continued)	Month 6 (Primary analysis time point) - average of Weeks 23 to 27 Month 12 -average of Weeks 49 to 53	 Descriptive statistics of score, change and percent change at Month 6 and Month 12 in the FAS ANCOVA model of change from baseline with the two stratification factors and treatment group as factors and the corresponding baseline score as a covariate in the FAS
Worst FCS Symptom – item score and composite score	Baseline is defined as the worst during the screening period and up to Day 1. If all assessments during the period are missing, the baseline will be considered as missing	Weekly worst. If a patient has less than 4 assessments in a week, the weekly score will be considered as missing	 Descriptive statistics of score, change and percent change over time in the FAS Frequency of patients by abdominal pain category (no pain, mild, moderate and severe) over time in the FAS
		Month 6 (Primary analysis time point) - worst of Weeks 23 to 27	 Descriptive statistics of score, change and percent change at Month 6 and Month 12 in the FAS
		Month 12 -worst of Weeks 49 to 53	2. ANCOVA model of change from baseline with the two stratification factors and treatment group as factors and the corresponding baseline score as a covariate on FAS
			 Descriptive statistics of abdominal pain score, change and percent change at Month 6 and Month 12 in the subset of ITT patients who reported any abdominal pain (pain score > 0) at Baseline
			 ANCOVA model of change from baseline in abdominal pain score with the two stratification factors and treatment group as factors and the baseline score as a covariate in the subset of ITT patients who reported any abdominal pain (pain score > 0) at Baseline

ISIS 678354-CS3

Observed Data			
Endpoint	Baseline	Post-baseline	Analysis

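### The four-entry weekly minimum is applied to maxima as well as averages, so an observed symptom peak in a sparse diary week is excluded from the exploratory Month 6 and Month 12 worst scores

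*Combined protocol and SAP*

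**What the plan says.** The FCS symptom diary has four daily items, each scored 0-10 over the past 24 hours, plus a daily composite. SAP 4.11.3.3 forms two weekly summaries. One is the average. For the other, "the highest (worst) response in each week will also be determined and used for summary and analysis".

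The completeness rule is stated for weekly scores in general: "If patients complete less than 4 daily assessments in a week, then the weekly FCS symptom scores will be considered as missing". The observed-data table repeats it for the maximum: "Weekly worst. If a patient has less than 4 assessments in a week, the weekly score will be considered as missing". The same entry appears for the version that uses the two-week-recall baseline.

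The Month 6 worst is the worst of Weeks 23 to 27 and the Month 12 worst is the worst of Weeks 49 to 53. The imputation steps say that the Month 6 value "will be calculated from the non-missing weekly scores from Weeks 23 to 27", with the same wording for Weeks 49 to 53. Imputation starts only when nothing is left: "If all weekly scores during the period are missing, the missing score at the primary analysis time point will be imputed", using the nearest week within 30 days of the target day.

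Three other places bear on this:
- The worst diary baseline carries no weekly minimum: "Baseline is defined as the worst during the screening period and up to Day 1". It is missing only if every assessment is missing.
- SAP 4.2.4 (Visit Windows) takes the highest daily score in each window and states no minimum.
- Protocol 6.2.5 asks patients for at least four daily assessments per week.

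**The concern.** A completeness minimum makes sense for an average, because an average of one or two days may represent the week poorly. A maximum behaves differently. A recorded 9 establishes that the patient reached 9, and further entries that week could not undo it. Setting that week to missing removes known information and adds none.

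Baseline and follow-up are also handled differently. A sparse screening week still contributes its peak to the worst diary baseline, while a sparse follow-up week does not contribute to the Month 6 or Month 12 worst. Where that matters, change from baseline looks better than the diary supports.

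At stake is the accuracy of the worst item and composite analyses in SAP 4.11.3.3. If sparse weeks with high scores were more common in one arm, the arm comparison would move as well.

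**Working it through.** The plan states no figure for this rule, so there is nothing to reproduce. The check follows the rule through and then sizes it.

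**1. Direction.** Let S be all diary entries in the five-week window, and R the entries in weeks with at least four. R is a subset of S, so if R is not empty, max(R) ≤ max(S) ≤ true worst. Equality max(R) = max(S) holds when the highest observed value also occurs in a retained week.

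**2. Worked case (invented diary).** Four weeks with at least five entries each have a maximum of 3. The fifth week has three entries: 9, 8, 9. The worst baseline is 9.

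| | Month 6 worst | Change from baseline |
|---|---|---|
| SAP rule | 3 | 3 − 9 = −6 |
| All entries | 9 | 9 − 9 = 0 |

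Four weekly scores remain, so imputation is not triggered.

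**3. Logic check.** In 20,000 random five-week diaries (0-7 entries per week, scores 0-10), the rule gave a higher score than all entries 0 times, a lower score 2,540 times, and a missing score despite recorded entries 661 times. These counts confirm the direction; they do not estimate real frequencies.

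**4. Chance that an attack week has one to three entries.** The documents give no completion rate. Assume independent daily completion with probability q: P = Σ C(7,k) q^k (1−q)^(7−k) for k = 1 to 3. At q = 0.5, P = (7 + 21 + 35)/128 = 0.492.

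| q | 0.4 | 0.5 | 0.6 | 0.7 | 0.8 | 0.9 |
|---|---|---|---|---|---|---|
| P(1-3 entries) | 68% | 49% | 29% | 13% | 3% | 0.3% |

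**5. Loss per attack patient (simulated).** Assumptions: a 5-day attack scoring 7-10, background mean 1.5, completion 75% normally and 35% during the attack, 8,000 attack patients. The mean worst is 6.9 under the rule, 8.4 with all entries and 9.7 in truth. About one third lose their observed maximum, by 4.5 points on average, so the mean loss is 8.4 − 6.9 = 1.5 points. A repeat with 20,000 patients and two background distributions gave 6.7-7.0, 8.3-8.4 and 9.7, with 32% losing 4.3-5.0 points.

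**6. Effect on an arm mean.** Protocol 9.2, Table 4 gives 0.2-0.35 pancreatitis events per patient-year. Over 35 days:
- 0.2 × 35/365.25 = 0.019 and 0.35 × 35/365.25 = 0.034 events per patient.
- Expected attacks on placebo: 20 × 0.0192 = 0.4 (20 planned) to 23 × 0.0335 = 0.8 (23 treated).
- Using step 5: 0.019 × 1.5 = 0.03 to 0.034 × 1.5 = 0.05 points.
- Using step 4 with a 6-point loss and each attack confined to one week: 0.0192 × 0.126 × 6 = 0.01 (q = 0.7) to 0.0335 × 0.682 × 6 = 0.14 (q = 0.4).

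If other severe episodes raised the share of patients with an attack to 5%-20% (assumed), the same formula gives 0.05 × 0.126 × 6 = 0.04 to 0.20 × 0.682 × 6 = 0.82 points over q = 0.7 to 0.4.

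**The case against.** The strongest reply is that the effect is negligible on the plan's own event rate, falls on an exploratory endpoint outside the 28-step hierarchy of SAP 4.9.1.3, and rests on an assumed diary pattern. That stands as to size. No document says that entries fall during illness, and step 4 shows how much depends on it.

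A second reply is that the rule matches the protocol's diary requirement, and that a maximum tends to rise with the number of entries, so some minimum helps comparability. This has some force. But Protocol 6.2.5 asks patients to complete entries; it does not say that what they recorded should be discarded. Retained weeks can still hold anywhere from four to seven entries.

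A third reply concerns reading. The sentence on non-missing weekly scores sits among the imputation steps, and SAP 4.2.4 states no minimum. The observed-data analysis might therefore use every entry. However, the general rule has no exception for the worst, and the observed-data table repeats it for the weekly worst. At best the sections need reconciling.

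Four stronger readings are tempting, and the documents do not support them:
- **An attack week with few entries always lowers the score.** It does so only if that week holds the period's highest observed value. An attack may span two weeks with one retained, and about two thirds of simulated attack patients lost nothing.
- **The drug effect is biased toward zero.** That needs sparse, high-scoring weeks to be more common on placebo. The results summary reports abdominal pain in 8 of 23 placebo and 3 + 4 = 7 of 43 olezarsen patients, but these are whole-study counts with no link to the windows or to diary completion.
- **Using all entries is always closer to the truth.** If all five weeks are sparse, the imputed-data analysis takes a nearby week. A single low in-window entry replacing that value could be further off.
- **The trial loses its attacks.** Adjudicated pancreatitis, ER visits, hospitalizations and inpatient days are captured separately from the diary.

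**Conclusion.** The point holds as a minor flaw in derivation. An observed peak in a week with one to three entries is excluded from the Month 6 or Month 12 worst item and composite scores. With at least one week retained, the error has one sign: too low or unchanged relative to the recorded entries. If no week qualifies, the observed-data score is missing. The worst diary baseline has no weekly minimum, so the possible shift in change from baseline is toward apparent improvement. None of this needs an assumption about the data.

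The size does. At the protocol's pancreatitis rate, the arm-mean effect is likely hundredths of a point, reaching about 0.14 only under poor completion with each attack confined to one week. It would be larger if other severe symptom episodes behaved alike, but nothing in the documents quantifies those. The direction of any between-arm effect cannot be settled from the documents. Primary and secondary conclusions are unaffected.

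**What to change.** In SAP 4.11.3.3:
- Apply the four-entry minimum to weekly averages only.
- Where at least one week in the window has four or more entries, take the Month 6 and Month 12 worst item and composite scores as the maximum of all diary entries in Weeks 23-27 and Weeks 49-53.
- Where no week has four entries, keep the present trigger for the 30-day imputation in the imputed-data analysis, but do not let the result fall below the highest in-window entry. Word the trigger by entry count, since a sparse week would no longer have a missing worst score.
- Tabulate the number of entries per window by arm, so that uneven completion is visible.
- Reconcile SAP 4.2.4 with the text and tables of 4.11.3.3.

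The cost is a few sentences and a small programming change. The downside is that some maxima will rest on uneven numbers of entries. Peaks on days with no entry remain unrecoverable: in the step 5 simulation, 9.7 − 8.4 = 1.3 points of the 9.7 − 6.9 = 2.8-point shortfall would remain.

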4.11.3.4. FCS impacts

The FCS Impacts Questionnaire includes 13 items addressing potential impacts of FCS on patient functioning. These 13 items ask patients to rate the frequency of each impact in the past 7 days during the screening period and at each study visit using the following scale: Never = 0, Rarely = 1, Sometimes = 2, Often = 3, and Always = 4. Higher scores denote more severe impacts.

An impacts composite score will be calculated as the average of the non-missing scores across the 13 impact individual items. If more than 50% of the questions are missing, the impacts composite score will be considered as missing for the visit.

Item-level scores, impacts composite score and their changes from baseline will be summarized by treatment group over time using descriptive statistics.

The change from baseline in the impacts composite scores at the primary analysis time point (average of Weeks 23, 25 27) and at Month 12 (average of Weeks 49, 51 and 53) will be analyzed using an ANCOVA model with the two randomization stratification factors and treatment group as factors and baseline score as a covariate, and will be conducted in the FAS.

In addition to the analyses described above based on the observed data, the missing values will be imputed. The change from baseline in the impacts composite scores at the primary analysis time point and at Month 12 based on the imputed data will be analyzed using an ANCOVA model with the two randomization stratification factors and treatment group as factors and baseline score as a covariate, and will be conducted in the FAS.

The missing values will be imputed as follows:

- For patients with a missing baseline value, their baseline score will be imputed using the average of non-missing data from other patients in the same stratification category. In the event of no observed data for imputation, history of pancreatitis will be used as the only classification factor for the purpose of identifying non-missing data for imputation. Additional factors, such as age and gender may be considered to further classify the imputation categories if supported by data.
- The Month 6 (primary analysis time point) score will be calculated from the non-missing scores from Weeks 23, 25 and 27 and the Month 12 score will be calculated from the non-missing scores from Weeks 49, 51 and 53. If all weekly scores during the period are missing, the missing Month 6 score will be imputed using the data from the week that is the closest to Day 169 and within $a \pm 30$ days window, the missing Month 12 data will be imputed using the data from the week that is the closest to the Day 351 and within $a \pm 30$ days window. If 2 or more visits with equal distance, then the average will be used.

ISIS 678354-CS3

Statistical Analysis Plan

The tables below list the summaries and analyses to be performed for the FCS impact score

Observed data			
Endpoint	Baseline	Post-baseline	Analysis
FCS Impacts – item score and composite score	Baseline is defined as the last non-missing assessment on or prior to the Day 1	If data is not available in a visit, the score will be considered as missing	Descriptive statistics of score, change and percent change over time in the FAS
		Month 6 (Primary analysis time point) - average of Weeks 23, 25, 27	1. Descriptive statistics of the impacts composite score, change and percent change at Month 6 and Month 12 in the FAS
		Month 12 -average of Weeks 49, 51 and 53	2. ANCOVA model of change from baseline in the impact composite score with the two stratification factors and treatment group as factors and the baseline score as a covariate in the FAS

Imputed data			
Endpoint	Baseline	Post baseline	Analysis
	Baseline is defined as the last non-missing assessment on or prior to the Day 1. If all pre-dose composite scores are missing, the baseline composite score will be considered as missing. Missing baseline will be imputed using the average of non-missing data from	Month 6 (Primary analysis time point) – average of Weeks 23, 25, 27 Month 12 -average of Weeks 49, 51 and 53 If all composite scores during the period are missing, the missing Month 6 score will be imputed using the data from the visit that is the	 Analysis Descriptive statistics of the impacts composite score, change and percent change at Month 6 and Month 12 in the FAS ANCOVA model of change from baseline in the impact composite score with the two stratification factors and treatment group as factors and the baseline score as a covariate in the FAS
	other patients in the same stratification category	closest to Day 169 and within a ± 30 days window, the missing Month 12 data will be imputed using the data from the week that is the closest to the Day 351 and within a ± 30 days window. If 2 or more visits with equal distance, then the average will be used.	

4.11.3.5. PROMIS Patient Reported Outcome Assessments

• The PROMIS Pain Interference Short Form 8a contains 8 questions to assess self-reported consequences of pain on relevant aspects of patients' life over the past seven days. This includes the extent to which pain hinders engagement with social, cognitive, emotional, physical, and recreational activities. The pain interference score will be calculated by summing the values of the response to each question to get a raw

score, then converting the raw score to a T-score using the PROMIS scoring manual. The T-score rescales the raw score into a standardized T-score with a mean of 50 and a SD of 10. A T-score of 50 is the average of the United States general population. Higher interference pain scores indicate a more severe impact of pain on a patient's life. If more than 50% of the questions are missing, the pain interference score will be considered as missing for the visit. If less than or equal to 50% of the questions are missing, the missing items will be imputed using the average of the non-missing items and rounded to the nearest integer.

The PROMIS 29+2 Profile v2.1 (PROPr) contains seven PROMIS domains (Physical Function, Anxiety, Depression, Fatigue, Pain Interference, Sleep Disturbance, and Ability to Participate in Social Roles and Activities), an additional pain intensity 0-10 numeric rating scale (NRS), plus two Cognitive Function Abilities items. The PROPr score will be calculated as:

- summing the values of the response to each question to get a raw total score for each domain. If more than 50% of the questions in a domain are missing, the domain score will be considered as missing for the visit. If less than or equal to 50% of the questions in a domain are missing, the missing items will be imputed using the average of the non-missing items in the same domain and rounded to the nearest integer.
- converting the raw domain scores to T-scores using the PROMIS scoring manual. A T-score of 50 is the average of the United States general population. Higher symptom scores indicate increased symptom burden and higher function scores indicate better functioning.
- converting the T-scores to theta values: theta = (T 50)/10, applying SAS code using theta values to calculate a PROPr score. The code is named "MAUT" (Multi-Attribute Utility Theory) and is availablithub.com/janelhanmer/PROPr. The PROPr scores range from 0 (as bad as dead) to 1 (perfect or ideal health).
- The PROMIS Cognitive Function Short Form 4a contains 4 questions to assess patient-perceived cognitive deficits over the past seven days. The cognitive function score will be calculated by summing the values of the response to each question to get a raw score, then converting the raw score to a T-score using the PROMIS scoring manual. A T-score of 50 is the average of the United States general population. Higher cognitive function scores indicate better cognitive functioning. If more than 50% of the questions are missing, the cognitive function score will be considered as missing for the visit. If less than or equal to 50% of the questions are missing, the missing items will be imputed using the average of the non-missing items and rounded to the nearest integer.

The pain interference score, PROPr domain and total scores, and cognitive function score will be summarized by treatment group over time using descriptive statistics. The changes from baseline at the primary analysis time point (average of Weeks 23, 25, 27) and at Month 12 (average of Weeks 51 and 53 for PROPr domain and total scores and cognitive function scores, average of Weeks 49, 51 and 53 for pain interference) will be analyzed using an ANCOVA model with the two randomization stratification factors and treatment group as factors and the corresponding baseline score as a covariate, and will be conducted in the FAS.

In addition to the analyses described above based on the observed data, the missing values will be imputed. The changes from baseline at the primary analysis time point and at Month 12 based on the imputed data will be analyzed using an ANCOVA model with the two randomization stratification

factors and treatment group as factors and the corresponding baseline score as a covariate, and will be conducted in the FAS. The missing values will be imputed as follows:

- For patients with a missing baseline value, their baseline score will be imputed using the average of non-missing data from other patients in the same stratification category. In the event of no observed data for imputation, history of pancreatitis will be used as the only classification factor for the purpose of identifying non-missing data for imputation. Additional factors, such as age and gender may be considered to further classify the imputation categories if supported by data.
- The Month 6 (primary analysis time point) score will be calculated from the non-missing scores from Weeks 23, 25 and 27, the Month 12 pain interference score will be calculated from the non-missing scores from Weeks 49, 51 and 53, and the Month 12 PROPr domain and total scores and cognitive function score will be calculated from the non-missing scores from Weeks 51 and 53. If all scores during the period are missing, the missing Month 6 score will be imputed using the data from the week that is the closest to Day 169 and within a ± 30 days window, the missing Month 12 PROPr domain and total scores and cognitive function score will be imputed using the data from the week that is the closest to Day 169 and within a ± 30 days window, the missing Month 12 PROPr domain and total scores and cognitive function score will be imputed using the data from the week that is the closest to the Day 351 and within a ± 30 days window. If 2 or more visits with equal distance, then the average will be used.

The tables below list the summaries and analyses to be performed for the PROPr domain and
total scores, pain interference score, and cognitive function score

Observed data			
Endpoint	Baseline	Post-baseline	Analysis
PROMIS 29+2 domain and total scores, cognitive function scores	Baseline is defined as the last non-missing assessment on or prior to Day 1	If data is not available in a visit, the score will be considered as missing	Descriptive statistics of domain and total scores, change and percent change over time in the FAS
		Month 6 (Primary analysis time point) - average of Weeks 23, 25, 27	1. Descriptive statistics of the domain and total scores, change and percent change at Month 6 and Month 12 in the FAS
		Month 12 -average of Weeks 51 and 53	2. ANCOVA model of change from baseline in the domain and total scores with the two stratification factors and treatment group as factors and the corresponding baseline score as a covariate in the FAS

ISIS 678354-CS3

Observed data			
Endpoint	Baseline	Post-baseline	Analysis
Pain interference	Baseline is defined as the last non-missing assessment on or prior to Day 1	If data is not available in a visit, the score will be considered as missing	Descriptive statistics of score, change and percent change over time in the FAS
		Month 6 (Primary analysis time point) - average of Weeks 23, 25, 27 Month 12 -average of Weeks 49, 51 and 53	 Descriptive statistics of the scores, change and percent change at Month 6 and Month 12 in the FAS ANCOVA model of change from baseline with the two stratification factors and treatment group as factors and the corresponding baseline score as a covariate in the FAS

Imputed data			
Endpoint	Baseline	Post-baseline	Analysis
PROMIS 29+2 domain and total scores, cognitive function scores	Baseline is defined as the last non-missing assessment on or prior to Day 1. If all pre-dose scores are missing, the baseline score will be considered as missing. Missing baseline will be imputed using the average of non-missing data from other patients in the same stratification category	Month 6 (Primary analysis time point) - average of Weeks 23, 25, 27 Month 12 -average of Weeks 51 and 53 If all scores during the period are missing, the missing Month 6 score will be imputed using the data from the visit that is the closest to Day 169 and within $a \pm 30$ days window, the missing Month 12 data will be imputed using the data from the week that is the closest to the Day 358 and within $a \pm 30$ days window. If 2 or more visit with equal distance, then the average will be used.	 Descriptive statistics of the domain and total scores, change and percent change at Month 6 and Month 12 in the FAS ANCOVA model of change from baseline in the domain and total scores with the two stratification factors and treatment group as factors and the corresponding baseline score as a covariate in the FAS

ISIS 678354-CS3

Statistical Analysis Plan

Imputed data			
Endpoint	Baseline	Post-baseline	Analysis
Pain interference	Baseline is defined as the last non-missing assessment on or prior to Day 1. If all pre-dose composite scores are missing, the baseline composite score will be considered as missing. Missing baseline will be imputed using the average of non-missing data from other patients in the same stratification category	Month 6 (Primary analysis time point) - average of Weeks 23, 25, 27 Month 12 -average of Weeks 49, 51 and 53 If all composite scores during the period are missing, the missing Month 6 score will be imputed using the data from the visit that is the closest to Day 169 and within $a \pm 30$ days window, the missing Month 12 data will be imputed using the data from the week that is the closest to the Day 351 and within $a \pm 30$ days window. If 2 or more visits with equal distance, then the average will be used.	 Descriptive statistics of the score, change and percent change at Month 6 and Month 12 in the FAS ANCOVA model of change from baseline with the two stratification factors and treatment group as factors and the corresponding baseline score as a covariate in the FAS

4.11.3.6. The Patient Global Impression of Severity Scale (PGIS) score and Patient Global Impression of Change (PGIC) Score

The PGIS score (scaled None = 0, Mild = 1, Moderate = 2, Severe = 3, and Very severe=4), change from baseline in PGIS, and PGIC score (scaled Much better = 1, A little better= 2, No change = 3, A little worse = 4, and Much worse =5) will be tabulated by severity or change category and by treatment group over time.

Change from baseline in PGIS at the primary time point (average at Weeks 23, 25, 27) and at Month 12 (average of Weeks 51 and 53) will be classified to 2 categories: improved (defined as change from baseline ≤ 0) and not improved (defined as change from baseline ≥ 0). The data will be analyzed using a logistic regression model with the two randomization stratification factors and treatment group as factors and baseline PGIS score as a covariate, and will be conducted in the FAS.

PGIC score at the primary time point (average at Weeks 23, 25, 27) and at Month 12 (average of Weeks 51 and 53) will be classified to 2 categories: improved (defined as PGIC score = Much better [< 1.5] or A little better [1.5 to < 2.5]) and not improved (PGIC score = No change [2.5 to < 3.5], A little worse [3.5 to < 4.5], Much worse [\geq 4.5]) and analyzed using a logistic regression model with the two randomization stratification factors and treatment group as factors and baseline PGIS score as a covariate, and will be conducted in the FAS.

